3.6.4.2. SECONDARY EFFICACY ENDPOINTS

Key secondary endpoints

Confirmatory hypothesis testing will be conducted for the key secondary endpoints. In order to control the rate of false positive conclusions with a family-wise error rate of 5%, a fixed

sequence approach will be applied. The key secondary endpoints are hierarchically ordered. This allows statistical testing for these endpoints at the same nominal significance level of 5% without adjustment, as long as the tests occur in the pre-defined sequential order, and given that all null hypotheses to be tested for endpoints with a higher rank (including the primary endpoint) are rejected. As soon as a test is not statistically significant for a certain endpoint, i.e. as soon as the sequence breaks, no confirmatory testing will be done for remaining endpoints lower in the ranking. Statistical comparison between the two treatment arms for the key secondary endpoints will be done by means of the following planned analyses (in hierarchical order):

1. Proportion of subjects with TTP-related death, a recurrence of TTP, or at least one treatment-emergent major thromboembolic event (e.g., myocardial infarction, cerebrovascular accident, pulmonary embolism or DVT) during the study drug treatment period (including extensions): Cochran-Mantel-Haenszel test with adjustment for severity of neurological involvement (stratification factor used in randomization). Subjects who have crossed over from placebo to caplacizumab will be evaluated in the initial treatment arm (placebo) only.
2. Proportion of subjects with a recurrence of TTP in the overall study period (including 4-week FU period): Cochran-Mantel-Haenszel test with adjustment for severity of neurological involvement (stratification factor used in randomization). Subjects who have crossed over from placebo to caplacizumab will be evaluated in the initial treatment arm (placebo) only.
3. Proportion of subjects with refractory TTP, defined as absence of platelet count doubling after 4 days of standard treatment, and LDH >ULN: Cochran-Mantel-Haenszel test with adjustment for severity of neurological involvement (stratification factor used in randomization). Subjects who have crossed over from placebo to caplacizumab will be evaluated in the initial treatment arm (placebo) only.

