4 GENERAL ASPECTS FOR STATISTICAL ANALYSIS

4.1 Analysis populations

This section contains a description of analysis populations considered for analysis of data from adult subjects.

Data of pediatric subjects will be analyzed separately from data of adult subjects. Given the limited number of pediatric subjects expected to be enrolled, and as all pediatric subjects will be enrolled in an open-label caplacizumab arm, the data will be analyzed descriptively, and no comparisons can be made or inferential statistics performed.

4.1.1 *All screened subjects population*

All subjects who signed an informed consent form.

4.1.2 *Intent-to-treat population*

All subjects who were randomized. The intent-to-treat (ITT) population will be used for general outputs and for main efficacy analysis.

4.1.3 *Modified intent-to-treat population*

All randomized subjects who received at least 1 administration of study drug, as randomized (cfr. Section 4.3.5). The modified ITT (mITT) population will be used for selected (sensitivity) analysis of efficacy.

4.1.4 *Per protocol population*

The per protocol (PP) population is a subpopulation of the ITT population, excluding those subjects who have had a major protocol deviation.

4.1.5 *Safety population*

All subjects who received at least 1 administration of study drug, as treated (cfr. Section 4.3.5). The safety population will be used for analysis of safety, PK, PD, disease markers, and immunogenicity data.

4.1.6 *Open-label Caplacizumab population*

All subjects who received at least 1 administration of open-label study drug. The open-label Caplacizumab (OL Caplacizumab) population will be used in cases where a separate analysis of open-label period is performed.

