6.1.2 Sensitivity analyses

The following sensitivity analyses will be performed:

- The primary endpoint analysis will be repeated on the mITT population
- The primary endpoint analysis will be repeated on the PP population.
- The primary endpoint analysis will be repeated on the ITT population with a constrained definition of time to platelet count response. For this analysis, scenarios 2, 5 and 8 will be considered as non response scenarios. The corresponding new censoring time are presented in Table 3 below.

Table 3: Constrained censoring and event plan (for scenarios 2, 5 and 8)

Scenario	Response	Censored	Time to event / censoring time (days)	Graphical representation (grey bar represents dPE)
2) Initial platelet count $\geq 150 \times 10^9/L$ at day x with subsequent stop of dPE within 5 days. Platelet count dropped below $150 \times 10^9/L$ between day x and stop of dPE on day y ($y \leq 45d$) and was not $\geq 150 \times 10^9/L$ by the stop of dPE	No	1	y	
5) Platelet count $\geq 150 \times 10^9/L$ at day x with subject early terminated within 5 days (on day y) while on dPE	No	1	y	
8) Platelet count $\geq 150 \times 10^9/L$ at day x with stop of dPE 5+ days later ($y > 0d$), platelet count stays $\geq 150 \times 10^9/L$ as of day x ($x+y \leq 45d$)	No	1	x+y+5	

- The primary endpoint analysis will be repeated on the ITT population with time to platelet count response defined as the first time platelet count is $\geq 150 \times 10^9/L$ without the requirement to stop daily PE within 5 days. Consequently, only subjects who have no platelet count $\geq 150 \times 10^9/L$ within 45 days of the first i.v loading dose of study drug after randomization, or who were early terminated before reaching platelet count $\geq 150 \times 10^9/L$ are censored for the analysis, with time of censoring at 45 days, or at time of early termination, whichever comes first. Time of stop of daily PE will have no

influence on reaching the endpoint or on censoring time. The scenarios are specified below in Table 4.

Table 4: Censoring and event plan (dPE stop within 5 days not required)

Scenario	Response	Censored	Time to event / censoring time (days)
1) Subject has event within 45 days, on day x.	Yes	0	x
2) Subject has no event within 45 days, and subject has no early termination within 45 days.	No	1	45
3) Subject has no event before early termination on day x, before day 45.	No	1	x

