Exacerbations and relapses will be documented as serious adverse events. Note that, exceptionally, daily PE may have been stopped before an initial platelet count $\geq 150 \times 10^9/L$ is reached, by investigator's decision. It is recognized that in this case the subject can still experience an exacerbation or relapse requiring re-initiation of daily PE if documented as described above.

- Treatment-emergent major thromboembolic event: e.g., myocardial infarction, cerebrovascular accident, pulmonary embolism or DVT, confirmed after adjudication (see below).

If a potential major thromboembolic event or TTP-related death occurs, the investigator will be requested to provide additional information for adjudication by a blinded independent committee. Only events that are confirmed after adjudication will be used for the analysis. More details are provided in CSP Section 3.4.3.6 and [Appendix B: Adjudication charter](#).

2. Proportion of subjects with a recurrence of TTP in the overall study period (including the FU period). A CMH test will be conducted with adjustment for GCS category (stratification factor used in randomization). For both treatment groups, only recurrences that have occurred prior to a potential switch to open-label caplacizumab will be evaluated for this analysis.
3. Proportion of subjects with refractory TTP, defined as absence of platelet count doubling after 4 days of standard treatment, and LDH $>$ ULN. A CMH test will be conducted with adjustment for GCS category (stratification factor used in randomization). Refractory TTP is derived as follows: (platelet count after 4 days of standard treatment / platelet count at start of standard treatment) $<$ 2 and LDH $>$ ULN after 4 days of standard treatment. Platelet count and LDH at Day 5 will be used for this analysis. Subjects who have reached platelet count response (primary endpoint) by Day 5 will not be considered as having a refractory TTP.

Subjects discontinued (lost to follow-up, withdrew consent, etc...) before day 5 will be excluded from the analysis.

CONFIDENTIAL

Missing values will be imputed using multiple imputation (Markov Chain Monte Carlo) by averaged simulated parameter values. The number of simulation iterations will be adapted to the proportion of missing values (0-10% missing values: 20 iterations, 10-20% missing values: 100 iterations) to keep the relative efficiency (RE) of multiple imputation under control (Rubin, 1987).

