The following sas code will be used as starting point for the multiple imputation:

```
proc mi data=original n impute=number seed=1 out=imputed minimum=0
round=1;
  by studyid trt01pn trt01p;
  mcmc impute=full;
  var _day1 _day2 _day3 _day4 _day5;
run;

where
ORIGINAL is the input dataset
IMPUTED is the data after imputation
NUMBER is the number of imputation depending on the percentage of
missingness
STUDYID is the study identifier
TRT01P and TRT01PN are respectively the categorical and numeric
versions of the planned treatment groups used for the subjects during
the DB treatment period
_DAYx (x=1 to 5) are the measurements for each subjects from day 1 to
day 5
```

4. Time to first normalization of all three organ damage marker levels, i.e. LDH, cTnI and serum creatinine. Time to first normalization of LDH, cTnI and serum creatinine is defined as: first time of LDH \leq ULN and cTnI \leq ULN and serum creatinine \leq ULN - time of first i.v. loading dose of study drug after randomization + 1 minute. The time to normalization will be represented by number of days with two decimal digits. Subjects in either initial treatment group who have switched to open-label caplacizumab before having reached the endpoint will be censored at time of switch. All on-treatment records during DB treatment period will be used. A stratified Log-rank test will be conducted based on a KM analysis with adjustment for GCS category and for an additional factor defining whether the subject has abnormal values at baseline for LDH only (not for cTnI or for serum creatinine) or not.

In addition to the confirmatory statistical tests, standard summary statistics will be provided for all key secondary endpoints. For the first key secondary endpoint 'proportion of subjects with TTP-related death, a recurrence of TTP, or at least one treatment-emergent major thromboembolic event during the overall treatment period (including extensions)' and for the second key secondary endpoint 'proportion of subjects with a recurrence of TTP in the overall study period' separate summary statistics will be included for the OL Caplacizumab treatment group. For these endpoints also the number of events will be reported.

All analyses will be run on the ITT population.

A detailed list of tables, listings and figures can be found in Section [14.2](#), Section [16.2](#) and Section [15.1](#), respectively.

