12 CHANGE FROM ANALYSIS PLANNED IN PROTOCOL

12.1 Changes before database lock

No shift tables for Vital signs are produced as they are not representing essential information that is not available elsewhere in the outputs.

In order to reduce any possible bias in the estimation of the effectiveness of Caplacizumab versus Placebo, the main efficacy analysis will be performed on the ITT population instead of

miITT. For the primary endpoint a separate analysis on miITT will be performed as sensitivity analysis.

Per protocol, all samples will be analyzed by a central laboratory, except for pregnancy, screening creatinine and samples of platelet count. However, some extra local laboratory creatinine samples have been analyzed for visits after screening. Those results will only be listed and will not be used for analysis. The extra local creatinine taken for safety reason will not be considered as protocol deviation. Those taken for reasons other than safety will be captured as protocol deviation. The same will apply for the extra PE assessments performed outside of the time point indicated in the schedule of assessment.

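### Refractory TTP (third key secondary endpoint): averaging the imputed draws amounts to single imputation, and the exclusion of subjects who leave before Day 5 has no stated rule for deaths and, in the readable text, no sensitivity analysis (minor)

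*SAP*

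**What the plan says.** The endpoint is the proportion of subjects with refractory TTP: less than a doubling of platelets after four days of standard treatment, together with LDH above the upper limit of normal (ULN). SAP 6.2.1 item 3 uses the Day 5 values and a CMH test adjusted for Glasgow coma scale (GCS) category.

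- **Early leavers:** "Subjects discontinued (lost to follow-up, withdrew consent, etc...) before day 5 will be excluded from the analysis".
- **Other gaps:** "Missing values will be imputed using multiple imputation (Markov Chain Monte Carlo) by averaged simulated parameter values", with 20 or 100 iterations depending on how much is missing.
- **Code:** it is introduced by "The following sas code will be used as starting point for the multiple imputation" and consists of one PROC MI call, by treatment arm, on the Day 1 to Day 5 measurements. No averaging, test or pooling step follows it.
- **Population:** "All analyses will be run on the ITT population", which SAP 4.1.2 defines as all randomized subjects.
- **Output:** Table 14.2.1.2.3 in SAP 14.2.2 is one frequency table with one CMH p-value.
- **Sensitivity analyses:** those in SAP 6.1.2 concern the primary endpoint, for example "The primary endpoint analysis will be repeated on the mITT population".
- **Protocol 3.6.4.2:** the endpoint is "defined as absence of platelet count doubling after 4 days of standard treatment, and LDH >ULN: Cochran-Mantel-Haenszel test", with no rule for missing data.

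**The concern.** Multiple imputation represents uncertainty about a missing value by several plausible values. The analysis is run on each completed data set and the results are then combined. If the draws are averaged first, each missing value becomes a single number close to its predicted mean. A threshold applied to that number gives one fixed yes or no. A subject with, say, a 25% chance of being refractory will usually be called not refractory, so the rate falls and the uncertainty disappears.

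The exclusion is a separate matter. It removes randomized subjects from an analysis labelled ITT because of something that happens after randomization and may be related to how ill they are. The rule ends in an open list. Protocol 3.2.3.2 groups death with loss to follow-up and withdrawal of consent as reasons for ending participation, so an early death could be dropped, yet no text says whether it is excluded, imputed or refractory.

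This is the third confirmatory test in a fixed sequence. If it fails, time to normalization of the organ damage markers is not tested confirmatorily.

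**Working it through.** **1. The plan's own figures.** SAP 3.2 gives no power for this endpoint. Its primary calculation does reproduce, which supports reading the drop-out as a constant hazard.
- Hazard ratio 4.2/7 = 0.60. Events = 4(1.960 + 0.842)²/(ln 0.60)² = 120.3, so 121.
- Drop-out hazard d = −ln(0.9)/10 per day. Event probability by 45 days = λ/(λ+d) × [1 − exp(−45(λ+d))], with λ = ln 2/median: 0.897 (placebo) and 0.940 (caplacizumab), mean 0.918.
- N = 121/0.918 = 131.7, so 132.

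**2. How many could be excluded.** 132 × (1 − 0.9^0.4) = 5.4 within four days and 132 × (1 − 0.9^0.5) = 6.8 within five, or about 3 per arm. This is an upper illustration. It is a planning input, Protocol 3.2.3.1 asks subjects who only stop study drug to return, and hospitalization is expected during daily plasma exchange.

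**3. Background rate.** Protocol 1.1 prints 19 refractory patients as 17% in a cohort of 133; 19/133 is 14.3%. Both are used.

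**4. CMH test on assumed counts.** Assume 66 per arm, 7 per arm with GCS ≤12 (1 placebo event, 0 caplacizumab), and 3 excluded per arm from the other stratum. Of the 63 kept per arm, 10 placebo and 3 caplacizumab subjects are refractory. In each stratum E = n₁m/N and V = n₁n₂m(N−m)/[N²(N−1)], where m is the number of events.
- GCS ≤12: observed 1, E = 0.5, V = 0.25.
- GCS 13-15: 56 per arm, 9 against 3, E = 6, V = 2.703.
- X² = (0.5 + 3)²/2.953 = 4.149, p = 0.042.

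Retaining the three excluded per arm:

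| Refractory among those retained | p |
|---|---|
| none | 0.042 |
| one per arm (X² = 12.25/3.361 = 3.645) | 0.056 |
| all six | 0.084 |
| the three placebo subjects only | 0.008 |
| the three caplacizumab subjects only | 0.29 |

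**5. Chance that p stays below 0.05** (independent binomials for the retained):

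| Refractory probability if retained | 3 excluded per arm | 1 excluded per arm |
|---|---|---|
| 14.3% in both arms | 65% | 86% |
| 17% in both arms | 60% | 83% |
| 30% in both arms | 44% | 70% |
| rates of the kept subjects (15.9% placebo, 4.8% caplacizumab, with 3 excluded) | 87% | 95% |

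Other starting points, with 3 excluded per arm (placebo against caplacizumab):
- 9 against 3 (p = 0.071): falls below 0.05 in 23-32%.
- 7 against 3 (p = 0.19): conclusion changes in under 1%.
- 10 against 2: stays significant in 83-99.7%.
- 12 against 3: stays significant in 91-99.6%.

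**6. Averaging.** In an illustrative log-normal model, averaging the draws lowered the proportion of imputed subjects classified as not doubling from 0.22 to 0.14 in one setting and from 0.30 to 0.20 in another, about a third.

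A trial-level simulation used 66 per arm and 4000 trials per setting. Platelets were log-normal (Day 1 median 25; log-SD 0.6 with correlation 0.8, or 0.8 with 0.7), and Day 5 LDH was above ULN in 70%. About 6 of 132 left early, at random or after a poor platelet rise; 5% of the others missed Day 5; 20 imputations were drawn.
- Null refractory rate: 14.0, 13.6, 13.9 and 13.4% with averaging, against 14.3, 13.9, 14.3 and 13.8% with pooling. The gap of 0.3-0.4 point is 0.003 × 63 = 0.19 to 0.004 × 63 = 0.25, or 0.2-0.3 subject per arm.
- Type I error: 4.3-5.9% with exclusion and averaging, 4.4-5.0% with complete data (Monte Carlo error 0.3-0.4 point).
- Leaving after a poor platelet rise: exclusion lowers both arms from 14.3% to 13.8-13.9%, about 0.3 subject per arm.

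Deaths were not simulated.

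**The case against.** Several points on the other side stand.

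- **General SAP rules.** SAP 4.2.2 leaves missing values out of percentage denominators, and 4.2.4 allows imputation only where specified. The exclusion follows that convention, and the platelet AUC in 6.2.2 uses the same pattern. The ITT label names the population; it does not by itself settle how missing outcomes are handled.
- **Undisclosed departure from the protocol.** A reader might infer this because SAP 12.1 reports that "the main efficacy analysis will be performed on the ITT population instead of" mITT and does not mention the exclusion. The documents do not support it. The protocol is silent on missing data for this endpoint, and its section 3.6.2 leaves the details to the SAP.
- **No sensitivity analysis anywhere.** This cannot be claimed. SAP 6.4 and 14.2.8 are unreadable in the public copy, so the statement is limited to the readable text.
- **No combining step at all.** A reader might infer this from the code. The SAP does write one, namely averaging. The fault is that it comes before the threshold and that no test result is pooled. Pooling may have been intended, but it is not specified.
- **Early deaths.** TTP-related deaths count in the first key secondary endpoint and all deaths in the mortality summary. That limits the harm but does not define this endpoint.
- **Assumed counts.** The case of 10 against 3 sits close to the boundary. The lower retention figures give early leavers the same risk in both arms, that is, no treatment effect among them.

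**Conclusion.** The point holds as a minor one, with moderate confidence. Averaging the draws is a stated rule, and it is the wrong one for a threshold endpoint, but at low missingness it costs only about 0.2-0.3 subject per arm. The exclusion is a defensible missing-data choice that lacks a rule for deaths and, in the readable text, a check. It can change the conclusion only when the result lies near 5%. Even then, three exclusions per arm is an upper illustration from the planning drop-out, because the documents give no rate of loss before Day 5.

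A reader might go further and conclude that the rule favours caplacizumab or inflates the type I error. The material does not show that. In the simulation both arms moved by the same small amount, and one of four settings (5.9%) exceeded 5% by more than simulation error. The direction of bias is not established. The refractory counts, the GCS split and the simulation model are all assumptions.

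**What to change.** 1. **Replace averaging.** Derive refractory status in each imputed data set, run the GCS-adjusted CMH test in each, combine by Rubin's rules (for example on the Wilson-Hilferty-transformed statistic), and label the p-value in Table 14.2.1.2.3 as pooled.
2. **Keep the main exclusion if wished, but complete it.** State how deaths before Day 5 are handled. Add one sensitivity analysis on all ITT subjects that retains non-death early discontinuations by imputation and counts deaths before Day 5 without platelet response as refractory. Add a tipping-point or best/worst-case check, because within-arm imputation alone does not explore the corner cases.

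Listing the exclusion in SAP 12.1 would be a courtesy. Imputing on the log scale and adding LDH to the model are optional. The separate descriptive refractory definition in 6.2.2 can stay as it is.

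**Cost:** SAP wording, a little programming, slightly wider error bars and no new data. Retaining early leavers and pooling, simulated with the optional log-scale and LDH model, gave a type I error of 3.2-4.6%, slightly conservative. Power was 46.5-47.4%, against 45.7-47.4% for the literal plan, at true rates of 14.3% and 4.5%.

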6.2.2 Other secondary efficacy endpoints

Other secondary efficacy endpoints are defined in Section [3.3.2.2](#).

In general, all endpoints will be summarized using descriptive statistics such as number of observations, means, standard error, and proportions, as appropriate. All analyses will be run on the ITT population.

- Proportion of subjects with at least one treatment-emergent major thromboembolic event (e.g., myocardial infarction, cerebrovascular accident, pulmonary embolism or DVT), confirmed after adjudication, as well as the number of such events, during the overall treatment period (including extensions) (Caplacizumab, Placebo, OL Caplacizumab).
- Proportion of subjects with recurrences of TTP as well as the number of such events during study drug treatment (including extensions) and after study drug treatment (during FU) will be summarized by treatment group (Caplacizumab, Placebo, OL Caplacizumab).
- Proportion of subjects with treatment-emergent clinically significant TTP-related events, as well as the number of such events in the overall study period (including 4-week FU period) as defined in Section [3.3.2.2](#) will be summarized by treatment group (Caplacizumab, Placebo, OL Caplacizumab).
- Area under the curve (AUC) of platelet count until Day 5, truncated at $150 \times 10^9/\text{L}$ if platelet count is $150 \times 10^9/\text{L}$ or above, will be summarized by treatment group (Caplacizumab, Placebo). The AUC value will be calculated using the linear trapezoidal rule, i.e. $AUC_{t_i \text{ to } t_{i+1}} = 1/2 * (C_i + C_{i+1}) * (t_{i+1} - t_i)$ where C_i is the platelet count at time point t_i . Missing platelet counts will not be imputed separately as missing values can be bridged by using the trapezoid rule on neighboring (available) timepoints, thereby implicitly interpolating the missing timepoint. If the subject discontinued prior to Day 5, the subject will not be considered in this analysis. Descriptive statistics will include the 25%, 75% and 90% percentiles.
- Mortality rate (number and percentage) will be summarized by treatment group (Caplacizumab, Placebo, OL Caplacizumab) during DB treatment daily PE period (OL Caplacizumab not applicable), overall treatment period, FU period and overall study period.
- Organ damage markers:
 - Time to LDH $\leq 1 \times \text{ULN}$
 - Time to cTnI $\leq 1 \times \text{ULN}$
 - Time to serum creatinine $\leq 1 \times \text{ULN}$

A separate KM analysis for each organ damage marker will be conducted with time to first normalization as dependent variable and treatment group (Caplacizumab, Placebo) as independent variable. Subjects in either initial treatment arm who have switched to open-label caplacizumab before having reached the endpoint will be censored at time of switch.

Time to first normalization of *organ damage marker* is defined as: first time of *organ damage marker* \leq ULN - time of first i.v. loading dose of study drug after randomization + 1 minute. All on-treatment records during DB treatment period will be used. The time to first normalization will be represented by number of days with two decimal digits.

- Proportion of subjects with increases in organ damage markers (cTnI and serum creatinine) above $1 \times$ ULN will be summarized by treatment group (Caplacizumab, Placebo, OL Caplacizumab) during DB treatment daily PE period (OL Caplacizumab not applicable), overall treatment period, FU period and overall study period.
- AUC of cTnI above $1 \times$ ULN (cTnI peak) will be summarized by treatment group (Caplacizumab, Placebo, OL Caplacizumab) during DB treatment daily PE period (OL Caplacizumab not applicable) and during overall treatment period. The AUC value will be calculated by the linear trapezoidal rule. The analysis will be repeated including and excluding cTnI peaks at baseline. Descriptive statistics will include the 25%, 75% and 90% percentiles.
- Proportion of subjects with neurological symptoms based on neurological assessment on Day 1, 2, 3, 4, 5 and Weeks 1 and 5 of 30-day post-daily PE treatment period, and the first and final FU visit will be summarized by treatment group (Caplacizumab, Placebo, OL Caplacizumab).
- Actual value and change from baseline in Standardized mini mental state examination (SMMSE) total score on Days 1, 2, 3, 4, 5 and Weeks 1 and 5 of the 30-day post-daily PE treatment period, and the first and final FU visit will be summarized by treatment group (Caplacizumab, Placebo, OL Caplacizumab). For the OL Caplacizumab treatment group change from baseline is based on the Day 1 assessment of the open-label treatment period.
- Proportion of subjects with evidence of cardiac ischemia and/or arrhythmia/conduction abnormalities on Days 1, 2, 3, and 4, and Weeks 1 and 5 of 30-day post-daily PE treatment period, and the first and final FU visit will be summarized by treatment group (Caplacizumab, Placebo, OL Caplacizumab).
- Proportion of subjects who have a platelet count $\geq 150 \times 10^9/L$ on Day 1, 2, 3, 4, 5 and Day 10 and end of study drug treatment (i.e., last weekly visit during the DB or OL treatment period) will be summarized by treatment group (Caplacizumab, Placebo, OL Caplacizumab).
- Proportion of subjects with refractory TTP, defined according to Scully et al. (2016) as lack of sustained platelet count increment or platelet counts $< 50 \times 10^9/L$ and persistently raised LDH ($> 1.5 \times$ ULN) despite 5 plasma exchanges and steroid treatment will be summarized by treatment group (Caplacizumab, Placebo). Refractory TTP is derived as follows: (platelet count at Day x $<$ platelet count at Day x-1 for at least 1 value of x with x=2,...,5) and (LDH $> 1.5 \times$ ULN from Day 1 to Day 5). Subjects who have reached platelet count response (primary endpoint) by Day 5 will be considered as not refractory to TTP. Missing values will be imputed by using multiple imputation (Markov Chain Monte Carlo) by

averaged simulated parameter values, except if the subject discontinued prior to Day 5. In that case, the subject will not be considered in the analysis.

- Time to stop of daily PE: A KM analysis will be conducted with time to stop of daily PE within the DB treatment period as dependent variable and treatment group (Caplacizumab, Placebo) as independent variable. Time to stop of daily PE is defined as: date of daily PE stop - date of first i.v. loading dose of study drug after randomization + 1 day.
- The number of PE days and the total PE volume (absolute and normalized) in the DB treatment daily PE period and the overall treatment period will be summarized by treatment group. For this analysis the treatment groups are defined as
 - Caplacizumab + OL Caplacizumab
 - Placebo + OL Caplacizumab

Subjects will thus be analyzed according to their initial treatment group, both before and after switch to open-label caplacizumab. The number of PE days is defined as the total number of days on which PE is documented. The absolute total PE volume is given by the sum over all PE days of the amount exchanged in liter, while the normalized total PE volume is calculated as the sum over all PE days of the multiple of plasma volume exchanged.

- Number of days in ICU and in hospital will be summarized by treatment group (Caplacizumab + OL Caplacizumab, Placebo + OL Caplacizumab) in the DB treatment daily PE period, in the overall treatment period, in the FU period and in the overall study period. The number of days in ICU is calculated as (ICU discharge date – ICU admission date + 1 day) summed over all stays in ICU. The number of days in hospital is calculated as (discharge date – admission date + 1 day) summed over all hospitalizations (including days in ICU). Subjects will be analyzed according to their initial treatment group, both before and after switch to open-label caplacizumab.

A detailed list of tables, listings and figures can be found in Section [14.2](#), Section [16.2](#) and Section [15.1](#), respectively.

